**Study 2: Higher 3-hydroxycotinine (3-HC)/cotinine is associated with greater reward and heart rate increases from intravenous nicotine:** In previous studies, high nicotine metabolite ratio (3-HC/cotinine) predicted poor outcomes for smoking cessation treatment with nicotine patch. The underlying mechanisms that associate metabolite ratio with treatment outcomes have not been fully elucidated. A total of 100 smokers were divided into quartiles based on their baseline plasma nicotine metabolite ratio. Following overnight abstinence, smokers received saline followed by escalating intravenous doses of nicotine (7 and 14 mcg/kg) given 30 min apart. Smokers in the first quartile (slower metabolizers) had lower FTND scores, suggesting lower levels of dependence. In contrast, smokers in the fourth quartile (faster metabolizers) reported greater craving for cigarettes following overnight abstinence from smoking and reported greater ratings of nicotine-induced good drug effects, drug liking, and wanting more drug. Higher nicotine metabolite ratio was also associated with greater heart rate increases in response to nicotine. These results suggest that nicotine metabolite ratio may influence the subjective rewarding and physiological effects from nicotine and withdrawal severity.

**Figure 2. Subjective ratings of the pleasurable and aversive effects of intravenous nicotine in smokers.** Shown is the mean value ( $\pm$  SEM) for 6 post-infusion ratings of drug effects for subjects ( $n=26$ ). The subjective ratings for nicotine are relative to the ratings for saline, using the DEQ with a scale of 0-10.

Further, all nicotine doses

In summary, our previous work demonstrates the feasibility of IV nicotine self-administration to determine the reinforcement threshold for nicotine in LITS. Our findings point to a range of nicotine doses, 1.5 to 6.0 mcg/kg, that is well-tolerated by non-dependent smokers and can be used to determine the reinforcement threshold. Our group has unique expertise and a track record in conducting IV nicotine administration studies in both male and female smokers.

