Sampling: In each of the five test sessions, subjects will be randomly assigned to one of the five doses of nicotine: 0.0125, 0.025, 0.05, 0.1 and 0.2 mg/70 kg. Subjects will first receive saline and the assigned nicotine dose in a randomized order and double-blind fashion. Subjects will be informed that they will be receiving drug A or B, which may be nicotine or saline. This procedure will allow subjects to sample the nicotine and saline that will be available during that session. In addition, subjective and physiological responses to the sample nicotine dose and saline will be assessed.

Nicotine Choice procedure: Beginning 15 minutes after the sampling phase is completed, subjects will be asked to make a choice between drug A or B every 15 minutes for a total of ten choices over 150 minutes. The drug chosen by the subjects will be immediately delivered with the infusion pump over 30 sec in 5 ml of saline. This choice procedure has been used in our IV nicotine self-administration study as well as in many previous studies with various drugs of abuse (Sofuoglu et al. 1999, 2000, 2001; 2009c). One particular advantage of this model, compared to the ad lib models used in previous IV nicotine self-administration studies (Harvey et al. 2004; Rose et al. 2003), is the ability to control amount of nicotine delivered without interfering with the self-administration behavior.

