## **12. Data analysis methods:**

Data analyses: The primary analyses will be intent-to-treat and will include all available data on subjects who complete at least one test day. Mixed-effects models will be used to test the study hypotheses. These models allow for different numbers of observations per subject, use all available data on each subject, and are unaffected by randomly missing data. They also provide flexibility in modeling the correlation structure of the data. All data will be checked for normality and transformations will be applied as necessary. Significance level of 0.05 will be used for the main hypotheses and Bonferroni correction will be applied for post-hoc tests and secondary analyses.

Specific Aim #1: Aim #1: To assess the threshold reinforcing dose and dose-effect curve for IV NSA at low doses in young adult LITS. Hypothesis #1A: The threshold reinforcing doses for IV NSA will be between 0.0125 to 0.05 mg/70 kg. Hypothesis #1B: The dose-effect curve for NSA will differ between males and females with relatively flat curve in female smokers.

**Aim #1 Analysis:** The reinforcing effects of nicotine will be determined by the number of IV NSAs in each session, ranging from 0 to 10. The threshold dose for NSA will be determined by the lowest dose of nicotine for which the number of NSAs is significantly greater than those for placebo (saline) (i.e., proportion of NSA significantly higher than 0.5). For assessing the dose-response relationship, the parameters of interest will be the slope and shape of the dose-response curve. The slope indicates the degree to which self-administration changes with an increase in nicotine dose (in other words, sensitivity of NSA to changes in nicotine dose).

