**Aim 2 Analysis:** The subjective-positive effects of nicotine which will be determined by the main dependent variables of scores on the "like the drug" and "want more drug" items of the Drug Effects Questionnaire, ranging from 0 to 100. The negative aversive effects of nicotine will be determined by the "dislike the drug" and "lightheaded/dizzy" item of the DEQ. The analysis for Specific Aim #2A will be similar to the analysis described for Specific Aim #1A except that the dependent variables will be continuous and thus we will use random effects linear regression. Gender effects will be explored also as outlined for Specific Aim #1B. Prior to analysis, we will also assess the distribution of the DEQ items and apply transformations as necessary. Furthermore, the mean ratings at each dose will be compared to 0. To assess the

relationship between nicotine reinforcement and positive subjective effects, and between nicotine reinforcement and negative subjective effects (Specific Aim #2B), we will use mixed effects models with the proportion of NSAs per session as the dependent variable, positive (negative) subjective effects in response to the sample dose as the main predictor of interest (in separate models for positive and negative effects). Nicotine dose, gender and the interactions among subjective effects, dose and gender will also be assessed. Non-significant interactions will be dropped from the models via backward elimination subject to the constraint that the models will be hierarchically well-formulated at each step. Statistically significant associations between subjective effects and NSA across doses and gender are expected but we will also explore whether these relationships vary by gender and dose.

**Exploratory Aim #1:** To examine the association between baseline 3HC/cotinine ratio and nicotine reinforcement threshold. To test this hypothesis, correlation analysis including 3 HC/cotinine ratio and nicotine reinforcement threshold will be performed in the total sample as well as in subgroups (male vs. female smokers).

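### Aim 2B relates choice of nicotine over saline to the nicotine sample's raw rating alone; adding the same-session saline rating as a covariate is a cheap improvement of uncertain size.

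*Combined protocol and SAP*

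**What the plan says.** Section 12, Aim 2 Analysis, specifies mixed-effects models "with the proportion of NSAs per session as the dependent variable" and "positive (negative) subjective effects in response to the sample dose as the main predictor of interest", in separate models for positive and negative effects. It continues: "Nicotine dose, gender and the interactions among subjective effects, dose and gender will also be assessed". The items are scored on a raw 0 to 100 scale, and no difference from saline is defined.

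The outcome is relative to saline. In Section 11.E subjects are "asked to make a choice between drug A or B every 15 minutes for a total of ten choices", one being nicotine and the other saline, under blind labels. Section 12, Aim #1 Analysis, judges reinforcement by whether the result is a "proportion of NSA significantly higher than 0.5".

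The saline rating is available. Section 11.E says that "subjective and physiological responses to the sample nicotine dose and saline will be assessed", and the footnote to Table 1 confirms that the same measures follow saline and nicotine. The pilot used it: the Figure 2 legend under Preliminary Studies says "The subjective ratings for nicotine are relative to the ratings for saline".

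**The concern.** The outcome compares nicotine with saline, but the predictor describes only one side of that comparison. A subject who rates both samples 60 enters the model as a strong responder, although nothing separates the two infusions for that person. A subject who rates nicotine 30 and saline 0 enters as a weaker responder, although the contrast is larger.

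Two things can follow. If background responding (rating style, that day's mood, withdrawal or expectancy) has no bearing on choice, it is noise in the predictor and pulls the coefficient toward zero, so a real link may be missed. If background responding also affects choice, the raw rating picks up that link, and the model can credit to nicotine something that saline produces equally. The doses are chosen near or below the expected threshold, where the drug's share of the rating is likely to be smallest.

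This is separate from Aim 2A's comparison of mean ratings with 0. Changing that reference would leave the Aim 2B regression as it is.

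**Working it through.** **The plan's own figure.** Section 12 gives Aim 2 power only for the threshold tests: 72 subjects, d' = 0.34, two-sided 0.05, 80% power. The noncentrality is 0.34 × √72 = 2.885. The normal approximation gives Φ(2.885 − 1.960) = 82.3% and the t-test 81.2%, so the figure reproduces. No power is stated for Aim 2B.

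**Dilution.** Write the ratings as N = B + D + e for nicotine and S = B + e′ for saline, where B is shared background, D the drug effect, and e and e′ independent noise of equal variance. Ignoring clustering, the slope on D is multiplied by:

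- raw rating: var D / (var B + var D + var e)
- with S as covariate: var D / (var D + var e + var B·var e/(var B + var e))

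Assumed values: D has SD 0.7 between subjects and 0.7 between sessions, so var D = 0.98; noise SD is 0.5, so var e = 0.25.

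- No background: 0.98/1.23 = 0.797.
- Background 0.7 subject + 0.7 session (var B = 0.98): raw 0.98/2.21 = 0.443; with S, 0.98/1.429 = 0.686. Relative to no background: 0.56 and 0.86.
- Background 1.0 + 1.0 (var B = 2.00): raw 0.98/3.23 = 0.303; with S, 0.98/1.452 = 0.675. Relative: 0.38 and 0.85.

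A simulated random-intercept model gave mean slopes of 0.033 with no background, 0.020 and 0.014 for the raw rating, and 0.028 and 0.027 with S. The ratios are 0.61 and 0.42 (raw) and 0.85 and 0.82 (with S), close to the formula.

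**Power, first set of assumptions.** 72 subjects × 5 sessions × 10 choices, categorical dose, gender, subject random intercept, linear model on the proportion, 500 runs per setting, 0.2 logits per unit of D. The implied correlation is var B / √(var N · var S). The two power columns are for subject intercepts in choice with SD 0.5 and 1.0.

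| Background SD (subject + session) | Implied N-S correlation | Power without → with saline, SD 0.5 | SD 1.0 |
|---|---|---|---|
| 0 | 0 | 93% → 94% | 79% → 78% |
| 0.3 + 0.3 (noise 0.7) | 0.17 | 85% → 85% | 69% → 69% |
| 0.7 + 0 | 0.43 | 88% → 90% | 82% → 83% |
| 0.7 + 0.7 | 0.59 | 78% → 90% | 58% → 74% |
| 1.4 + 0 | 0.74 | 79% → 90% | 73% → 76% |
| 1.0 + 1.0 | 0.74 | 60% → 88% | 44% → 73% |

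The last two rows have the same correlation. When the background is all stable, the gain is 11 and 3 to 4 points; when half of it varies by session, the gain is 28 and 29. The random intercept deals with much of the stable part but not with the session part.

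**Power, second set.** 0 to 100 scale: background SD 20, its common part 60% person and 40% session, 0.025 logits per point of drug effect, again with a subject random intercept. With drug-effect SD 12, two separate runs gave, without → with the saline rating:

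- correlation 0.3: 92% → 92% and 92% → 93%
- correlation 0.5: 92% → 96% and 94% → 95%
- correlation 0.7: 94% → 98% and 94% → 99%

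With drug-effect SD 8: 40% → 40%, 41% → 46% and 48% → 57% at the same correlations. With SD 12 and half the drug-effect variance between subjects, the gains were about 2, 6 and 13 points in one run, and about 6 to 20 points over correlations 0.5 to 0.7 in the other.

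**If background also drives choice.** With choice also following the shared background (0.012 logits per point assumed) and no drug-effect link at all, the raw-rating model rejected 30% to 60% of the time at correlations 0.5 to 0.7. With the saline rating added, it rejected 16% to 19% of the time.

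**Difference score.** With no shared background and noise SD 0.7, replacing N by N − S cut power from 72% to 56%. The covariate form cost about 1 point at most in the settings where choice followed the drug effect alone, which is within simulation error.

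**The case against.** The strongest reply is that the plan's model is a legitimate test of an association, and that its random intercept already handles rating style. Much of that stands. A reader might infer a large and certain loss of power, for instance from a binomial regression with clustered standard errors and no random intercept. The documents do not support that: Section 12 specifies mixed-effects models, and the Aim 1 text names subject as the random effect. Under such a model the gain is often small. A reader might also infer that the Aim 2B test is invalid as written. It is not, unless background responding itself affects choice, and the documents give no evidence on that either way.

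A second reply is that the covariate can lower power. When choice follows both the drug effect and the background, power fell from 69% to 65%, 88% to 78% and 97% to 87% at correlations 0.3, 0.5 and 0.7. The figures stand, but part of the higher power is the background link itself: the raw model rejects 30% to 60% of the time in that setting when nicotine has no link with choice.

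Third, the wording leaves some room. Hypothesis 2B speaks of the effects of IV nicotine, and the pilot scored ratings against saline, so a saline-referenced score may have been meant. The stated 0 to 100 range and the absence of any defined difference favour the raw reading.

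Fourth, the saline ratings may not all be collected as assumed. Section 11.C lists five DEQ items, and of the four that Section 12 analyses only liking is among them. This stands, and the fix must deal with it.

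**Conclusion.** As written, Aim 2B pairs a saline-referenced outcome with a predictor that is not saline-referenced, while the rating that would supply the reference is collected in the same session. This can dilute the H2B coefficient or, if background also tracks choice, inflate it. The power gain from adding the saline rating is about zero at low nicotine-saline correlation, a few points at moderate correlation, and about 5 to 20 points at high correlation or with large session-level background. The 28 to 29 points seen once needed a background variance about twice that of the drug effect, half of it varying by session.

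Every size here rests on assumed SDs, correlations and slopes, and on a linear random-intercept model for the proportion. If choice follows the nicotine rating regardless of saline, the plan loses nothing. The covariate also does not remove the second problem entirely, since a single saline rating measures background with error: 16% to 19% rejection is better than 30% to 60% but still above 5%. This is a cheap improvement, not an error that invalidates the analysis.

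**What to change.** In Section 12, Specific Aim #2B, add one sentence: each mixed model, positive and negative, includes the same item's rating of the saline sample from the same session as a covariate beside the nicotine sample rating, and H2B is tested on the nicotine-rating coefficient. Do not use a plain nicotine-minus-saline difference as the main predictor. Report the model without the saline rating as a sensitivity analysis. State the random effect explicitly for Aim 2B, and state which post-infusion DEQ time point or summary is used, the same for both samples.

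Reconcile the DEQ items in Section 11.C with those in Section 12, so that every analysed item is collected after both samples.

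The cost is one degree of freedom per model and a coefficient read as the effect at a given saline rating rather than marginally. No extra visit or procedure is needed for any item already collected after both samples; an item not now on the form would have to be added to it.

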## **7. Subjects:**

Inclusion criteria: 1) Female and male smokers, aged 18 to 35 years, who have been smoking for at least a year, and a life-time consumption of at least 100 cigarettes; 2) smoke more frequently than once a week and  $\leq 5$  cpd; 3) FTND score  $\leq 3$  indicating no or minimal evidence for nicotine dependence; 4) urine semi-quantitative cotinine levels  $> 100$  ng/mL indicating an active smoking status; 5) not seeking treatment at the time of the study for nicotine dependence; 6) in good health as verified by medical history, screening examination, and screening laboratory tests; 7) for women, not pregnant as determined by pregnancy screening, nor breast feeding, and using acceptable birth control methods.

Exclusion criteria: 1) history of major medical illnesses that the physician investigator deems as contraindicated for the subject to be in the study; 2) requirement of any form of regular psychotropic medication (antidepressants, antipsychotics, or anxiolytics) or psychiatric diagnosis and treatment for psychiatric disorders including major depression, bipolar disorder, schizophrenia in the past 6 months; and 3) current dependence to alcohol or any other recreational or prescription drugs and; 4) daily use of smokeless tobacco products or exclusive daily use of e-cigarettes (non-daily users will be included).

Justification for age criteria: The study will enroll young adults between the ages of 18 to 35 because this age group represents a critical time for development of nicotine addiction, with almost all progression to daily smoking completed by the age of 26.

Stratified sampling procedure for race and presence of daily smoking: The study will enroll 36 male and 36 female LITS. The two groups will be matched on race and presence of daily smoking. Race has been shown to influence smoking behavior and nicotine pharmacokinetics. We will create a race variable (0= Caucasian, 1= African-American, 2=Other) to match groups on race. We will also stratify for the presence of daily smoking because daily smoking may influence the behavioral effects from smoking by tolerance development (9-11). This approach will allow balancing the male and female smokers for light vs. intermittent smokers. A categorical variable will be created for the presence of daily smoking (1= present, and 0 = absent).

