We expect to observe a significant dose effect and will compare the proportion of NSAs at each dose to 0.5 across subject groups. The lowest nicotine dose that has a significantly higher proportion of NSA than 0.5 will be selected as the threshold dose (Hypothesis 1A). To assess the dose-response relationship in the preference for nicotine, polynomial effects of dose (linear, quadratic, cubic) and change-point linear models will be tested in the mixed effects logistic regression model. We anticipate that there will be a significant linear relationship between dose and response rate at lower doses with flattening of the relationship at higher doses. We will use the slope of the dose effect to assess the linear dose effect. Alternative non-linear dose response relationships will be considered if residual plots reveal significant deviations of the models from linearity. Gender differences in the shape of the curve for NSA will be examined in the logistic regression model by including gender main effect and its interactions with dose (Hypothesis 1B). Significant interactions between the group factors and dose will be considered supportive of systematic group differences in the dose-response relationships between groups. If significant interactions are observed, then separate thresholds and curves will be estimated within each subject group.

**Specific Aim #2:** To assess the threshold and dose-effect curve for the positive and negative/aversive subjective effects of IV nicotine at low doses and its relationship to nicotine reinforcement. Hypothesis #2 A: The threshold for the positive effects will be between 0.0125 to 0.1 mg/70 kg, for the negative/aversive effect it will be  $\geq 0.1$  mg/70 kg. Hypothesis #2B: Nicotine reinforcement will be positively correlated with the positive and negatively correlated with the negative/aversive subjective effects of IV nicotine.

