**Rationale for sample size:** Power for Specific Aims 1 and 2 is based on our preliminary studies comparing nicotine doses of 0.1, 0.2, 0.3 and 0.4mg to saline (34). We consider a difference between 50% (half of infusions in favor of nicotine) and 67% (two-thirds in favor of nicotine) as clinically meaningful. With our sample of 72 subjects we can detect such a proportion (67%) as statistically different from 50% with 80% power assuming two-sided test and alpha=0.05 (Specific Aim 1). Also with our sample of 72 subjects, we can detect medium effects ( $d'=0.34$ ) for the threshold tests on “good effects” and “drug liking” under the same assumptions (Specific Aim 2).

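### The test of Hypothesis 2B comes from a model pruned by backward elimination, with no contrast named if a rating interaction is kept, so its 0.05 level is not assured

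*Combined protocol and SAP*

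**What the plan says.** Section 12 states Hypothesis 2B as "Nicotine reinforcement will be positively correlated with the positive and negatively correlated with the negative/aversive subjective effects of IV nicotine". The Aim 2 Analysis tests it with mixed-effects models for the proportion of nicotine choices per session. The rating after the sample dose is the predictor of interest, and positive and negative ratings have separate models. On the remaining terms it says "Nicotine dose, gender and the interactions among subjective effects, dose and gender will also be assessed", followed by "Non-significant interactions will be dropped from the models via backward elimination". Elimination must respect hierarchy at every step, so a rating main effect is not dropped by this rule. The paragraph closes by expecting an association over doses and genders and by offering to explore whether it varies between them.

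On error control, the opening of Section 12 says "Significance level of 0.05 will be used for the main hypotheses and Bonferroni correction will be applied for post-hoc tests and secondary analyses". It does not list which hypotheses are main and which are secondary.

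Four things are not stated: the significance level for keeping an interaction, the coding of dose in this model (Aim 1 treats it as categorical), the contrast that tests Hypothesis 2B if a rating interaction survives, and any allowance for the selection.

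**The concern.** What the rating coefficient means depends on which terms survive. If every rating interaction is dropped, it is one common slope, which is what Hypothesis 2B describes. If one is kept and the factors are reference-coded, it is the slope at one reference dose, in one reference sex, or in one cell of both. That is a different quantity, and the data have chosen it. The selection also favours trials in which the dose- or gender-specific slopes happen to be spread out, so a single reference slope is more likely than usual to look significant.

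Two things are at stake: the false-positive rate of a numbered hypothesis under a Specific Aim, and comparability between its halves. The positive and negative models are pruned separately and could end up testing different quantities under one name.

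**Working it through.** **The plan's own figure.** The plan gives no power or detectable effect for Hypothesis 2B. The nearest figure is for the Aim 2 threshold tests: "with our sample of 72 subjects, we can detect medium effects", with d' = 0.34, 80% power and two-sided alpha 0.05.
- Normal approximation: d = (1.960 + 0.842)/√72 = 2.802/8.485 = 0.330.
- One-sample noncentral t: d = 0.335, with 81.2% power at d = 0.34.

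The figure reproduces, but it does not cover Hypothesis 2B.

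**Inputs from the documents.** Section 7: "The study will enroll 36 male and 36 female LITS". Sections 11 and 12: five doses per subject, ten choices per session, outcome 0 to 10, and a starting model with all interactions among rating, dose and gender.

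**Assumptions not in the documents.** Categorical dose with reference coding; retention level 0.05 or 0.10; within-subject correlation of ratings 0.4; between-subject SD 0.3 or 1.0 and session SD 0.5 on the logit scale; a random-intercept linear model for the proportion in place of a logistic one.

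**How often an interaction is kept by chance.** Three terms involve the rating: the three-way term (4 df), rating by dose (4 df) and rating by gender (1 df). If the three tests were independent, the chance of keeping at least one would be 1 − 0.95³ = 14.3% at 0.05, and 1 − 0.90³ = 27.1% at 0.10. The simulations agree with this.

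**Null simulation.** There was no rating effect in any dose or gender cell. Each setting had 4,000 trials; the Monte Carlo standard error near 5% is √(0.05 × 0.95/4000) = 0.34 points.

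| | SD 1.0, retain at 0.05 | SD 0.3, retain at 0.05 | SD 1.0, retain at 0.10 |
|---|---|---|---|
| Rating interaction kept | 15.4% | 14.3% | 27.7% |
| Reference-coded rating coefficient, selected model | 8.0% | 8.7% | 9.4% |
| Same coefficient, only trials with an interaction kept | 25.1% | 26.7% | 21.2% |
| Slope averaged over dose and gender, selected model | 5.1% | 5.8% | 5.1% |
| Rating coefficient, fixed model without interactions | 4.8% | 5.5% | 4.8% |
| Averaged slope, full model without selection | 5.1% | 5.3% | 5.1% |

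**Where the excess arises.** In the first setting, trials with a kept interaction contribute 0.1535 × 0.2509 = 0.0385. The rest contribute 0.0795 − 0.0385 = 0.0410, a rate of 0.0410/0.8465 = 4.8%. In the second setting, the same steps give 0.0867 − 0.143 × 0.2674 = 0.0485, and 0.0485/0.857 = 5.7%. The excess is therefore almost all in the minority of trials where the coefficient has changed meaning.

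**Sensitivity to the error model.** With independent errors and retention at 0.05, separate runs gave 7.3% to 7.9% for the reference-coded coefficient, and one of them gave 5.1% for the averaged slope. At 0.10 retention that version gave 9.7% and 5.9%. Further runs with 0-to-10 outcomes and random intercepts gave 7.5% to 8.6% at 0.05 for the reference-coded coefficient.

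**The case against.** The strongest reply is that the inflation comes from a coding choice the plan never makes. Its closing sentence expects an association over all doses and both genders, which reads most naturally as an overall slope. Tested as an average over dose and gender, that slope stays at about 5% to 6% even after elimination. The rule is also pre-specified and removes interactions only, and hierarchy protects the rating main effect. In about 85% of null trials no rating interaction survives, and the coefficient is then the common slope. All of this stands, and it rules out saying flatly that the 0.05 level is lost. It does not supply the missing contrast: the plan never says the averaged slope will be used, and reading off a reference-coded coefficient would be consistent with its wording.

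A reader might infer an error rate of 18% to 20%, the share of null trials with either a significant rating coefficient or a kept rating interaction. The documents do not support that as an error rate for Hypothesis 2B, because a kept interaction is not the stated correlation and Section 12 treats variation by gender and dose as exploration.

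A reader might also take Hypothesis 2B to be a main hypothesis at 0.05. It is numbered under a Specific Aim, apart from the Exploratory Aims. But Section 12 does not classify it, Section 4 names threshold dose and dose-response slope as the main outcomes, and Section 11 names the number of self-administrations. Its class is unclear.

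**Conclusion.** The concern holds in a limited form. The model for Hypothesis 2B is chosen on the same data that test it, and the test is undefined when a rating interaction is kept. With reference coding the false-positive rate for one rating model is about 8% to 9%, against about 5% for a fixed model. With an averaged slope it is about 5% to 6%. The 0.05 level is therefore not assured, rather than always lost.

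The sizes depend on the assumed coding, retention levels and variances, and on a linear approximation; the logistic mixed model was not simulated. The absence of a named contrast can be read from the text and needs none of these assumptions. The point affects one Aim 2 hypothesis and leaves the Aim 1 threshold analysis untouched.

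**What to change.** Remove backward elimination from the test of Hypothesis 2B. Name one contrast in advance and test it without selection, choosing one of:
- the rating coefficient in a model with categorical dose and gender and no interactions (null rate 4.8% to 5.5% above); or
- the rating slope averaged over dose and gender in the full, unselected model (5.1% to 5.3%).

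Use the same choice for the positive and negative models. Report rating-by-dose and rating-by-gender from a separate pre-specified model as exploratory; the Bonferroni rule that Section 12 sets for secondary analyses can be applied there. State whether Hypothesis 2B is main or secondary, so that its significance level is fixed.

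The cost is analysis-plan wording only, with no change to subjects, data or procedures. The downside is that a real interaction no longer alters the headline test and is reported only as an exploratory finding.
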